The estimated safe starting dose of MLN9708 will be selected from the dose-escalation portion of

the C16004 study, a phase 1 study of weekly dosing in patients with relapsed and refractory multiple myeloma. The starting dose will be at least 1 dose level below the C16004 MTD (if it has been reached by the time this study starts) and, if not, then a dose level completed without documented dose-limiting toxicity (DLT).

DLTs will be assessed in Cycle 1 only. In the context of emerging clinical data of single-agent MLN9708, dose-escalation of MLN9708 will continue until the MTD has been identified or a maximum planned dose (MPD) is determined to be safe.

Once the MTD/RP2D has been established, 2 expansion cohorts of patients with relapsed or refractory amyloidosis, including approximately 10 proteasome inhibitor-naïve patients and approximately 16 proteasome inhibitor-exposed patients, will be treated at the MTD/RP2D to more fully characterize the safety, tolerability, and efficacy of MLN9708, and the PK and pharmacodynamics of MLN9708 in this patient population. As many as 30 patients will be enrolled in the dose-escalation portion of the study, and as many as 20 additional patients (26 in total, including 6 patients from the dose-escalation portion) will be enrolled in the expansion cohorts.

Toxicity will be evaluated according to the investigators' documentation of adverse events (AEs) using the National Cancer Institute Common Terminology Criteria for Adverse Events, version 4.03. AEs will be assessed, and laboratory values, vital signs, and ECGs will be obtained to evaluate the safety and tolerability of MLN9708.

Patients will be evaluated at scheduled visits over 4 study periods: Screening, Treatment, End of Treatment (EOT), and Follow-up (progression-free and overall survival). Patients will discontinue treatment if they experience PD or unacceptable toxicity. The maximum duration of treatment with either single-agent MLN9708 or MLN9708 plus dexamethasone, however, will be 12 cycles unless after discussion between the investigator and the sponsor, it is determined that a patient would derive benefit from continued therapy beyond 12 cycles.

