Abbreviations: BNP = B-type natriuretic peptide; CT = computed tomography CXR = chest X-ray; ECG = electrocardiogram; ECOG = Eastern Cooperative Oncology Group; EMG = electromyography; EOT = end of treatment; Ig = immunoglobulin; INR = international normalized ratio; MRI = magnetic resonance imaging; NT-proBNP = N-terminal proBNP; OS = overall survival; PD = progressive disease; PFS = progression-free survival; PK = pharmacokinetics; PT = prothrombin time; PTT = partial thromboplastin time; QOL = quality of life; SPEP = serum protein electrophoresis; UPEP = urine protein electrophoresis.

a Evaluations including CT scans, MRIs, and skeletal surveys may be performed within 8 weeks of the first dose of study drug.

b One complete cycle is 28 days. In order to begin a new cycle of treatment, certain criteria must be met (see Section 6.5.2). Patients who do not continue study treatment dosing after Cycle 1 must complete the EOT and follow-up assessments.

c All evaluations/procedures are to be conducted on Day 1 of the stated cycle before dosing or within 3 days before the first dose of drug unless otherwise specified.

d Patients who do not continue treatment must complete the EOT assessments, which should occur at least 30 days after the last dose of study drug or prior to

Study Procedures	Screening ^a	Treatment Period					End of Treatment ^d	Follow-up	
		CYCLES 1 -12 ^b						PFS ^e (± 1 wk)	OS ^f (± 1 wk)
	Days	Days				Every 6 weeks		Every 6 weeks	Every 12 weeks
	-28 to -1	1 ^c	8	15	Rest Period 22 to 28	Every 6 weeks		Every 12 weeks	Every 12 weeks

the initiation of subsequent antineoplastic therapy.

- e Conducted from EOT until occurrence of PD or the initiation of subsequent antineoplastic therapy. If a patient comes off treatment due to PD, they should continue to be followed for OS long-term follow-up. Hematologic response assessments should be conducted every 6 weeks (± 1 week) during PFS follow-up while amyloid organ response assessments should be conducted every 6 months, including a neurologic examination in patients with persistent neurologic symptoms and clinical examinations in patients with persistent symptoms thought by the investigator to be amyloid-disease related (see Section 7.5.12).
- f Conducted every 12 weeks (± 1 week) after PD or the initiation of subsequent antineoplastic therapy. Data may be collected by methods that include but are not limited to telephone, e-mail, mail, and social security indexes.

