A 3 + 3 dose-escalation scheme will be implemented and dose intervals will follow those outlined in Section 6.4. Although DLTs may occur at any point during treatment, only DLTs occurring during Cycle 1 of treatment in the phase 1 portion will necessarily influence decisions regarding dose-escalation, expansion of a dose level, or evaluation of intermediate dose levels. In the context of emerging clinical data of single-agent MLN9708, dose-escalation of MLN9708 will continue until the MTD has been identified or a maximum planned dose (MPD) is determined to be safe. Based on experience with other drugs in this condition, it is considered unlikely that patients with systemic AL amyloidosis will tolerate doses higher than those tolerated in other diseases, such as multiple myeloma. Therefore, the maximum dose in patients with systemic AL amyloidosis may be the MTD as recommended from the phase 1 single-agent study of weekly MLN9708 in relapsed/refractory multiple myeloma (C16004). For treatment Cycle 2 and beyond, doses of MLN9708 may be held or reduced in an attempt to manage toxicity according to the guidelines outlined in Section 6.6.

More conservative dose-escalation, evaluation of alternative dosing, and expansion of an existing dose level are all permissible following discussions between the sponsor and the investigators, if such measures are needed for patient safety or for a better understanding of the dose-related toxicity, exposure, or pharmacodynamics of MLN9708.

Treatment repeats every 28 days for 3 cycles. If there is no hematologic response (PR, VGPR, or CR) after completion of 3 cycles of single-agent MLN9708, dexamethasone will be added at the initially recommended dose of 40 mg on Days 1 to 4 of every cycle (d1-4 q28days), beginning in Cycle 4. For patients with fluid retention > 3% of body weight despite optimal diuretic therapy, a starting dose of dexamethasone 20 mg should be considered. The patient's response status will be reassessed after 3 additional cycles; if there

is no hematologic response at that time, the patient will be removed from treatment and followed for survival.

If there is response with MLN9708 alone or dexamethasone and MLN9708, the patient may continue on study for up to 12 cycles of treatment in the absence of PD. Study treatment beyond 12 cycles is allowed only if clinical benefit is clearly indicated after a discussion between the Millennium clinician and the investigator treating the patient.

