Radiological evaluations and serial blood/urine samples will be employed to assess the status of the patient's amyloidosis. An evaluation of disease response using standardized criteria ^(53, 54) will be performed after each cycle during treatment and then at regular intervals during follow-up.

If patients are removed from treatment for unacceptable toxicity or reasons other than PD, they will continue in PFS follow-up until documented disease progression or the initiation of subsequent antineoplastic therapy. Once a patient experiences PD or starts subsequent antineoplastic therapy, they will proceed to the OS follow-up phase.

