4.3 Duration of Study

The duration of enrollment will be approximately 24 months.

Patients who have a response to treatment may remain on treatment for a maximum of 12 cycles or until the occurrence of PD or unacceptable toxicity, whichever occurs first. Patients who stop treatment for any reason other than disease progression will continue in PFS follow-up and be seen every 6 weeks until documented disease progression. After disease progression, all patients will continue to the OS follow-up part of the study and will be contacted every 12 weeks.

Delayed treatment-related AEs will be followed for 30 days after last dose of study drug or until initiation of subsequent antineoplastic therapy. The analyses for the clinical study report will be conducted after 75% of patients have PD or 12 months after last patient is enrolled, whichever occurs first in the study.

It is anticipated that this study will last for approximately 84 months. The duration of follow-up for overall survival will be 60 months after the last patient enters the study. Treatment may be continued in this study or in a MLN9708 rollover study, if and when such a study is made available, upon request by the investigator and agreement by the project clinician.

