7.5.17 Follow-Up Assessments (PFS and OS)

Patients who do not develop PD will continue to have PFS follow-up visits. The hematologic PFS follow-up should occur every 6 weeks from the EOT until the occurrence of progression or the start of subsequent antineoplastic therapy. A bone marrow aspirate and biopsy may be repeated at the discretion of the investigator as clinically indicated, but is not required during this follow-up period. The amyloid-organ PFS follow-up assessments should occur every 6 months from the EOT until the occurrence of progression (including hematologic progression) or the start of subsequent antineoplastic therapy. Refer to the [Schedule of Events](#) and Section 7.5.12 for appropriate assessments.

After the occurrence of PD or the initiation of subsequent antineoplastic therapy, patients will continue to have OS follow-up visits. The OS follow-up visits should be conducted every 12 weeks after documented PD or until the initiation of subsequent antineoplastic therapy. Data may be collected by methods that include, but are not limited to, telephone, e-mail, mail, and social security indexes. The duration of follow-up for OS will be 60 months after the last patient starts treatment.

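### The plan gives two follow-up rules for patients without hematologic response after Cycle 6; if the survival wording is applied, their progression data end at about 6 months

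*Protocol*

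**What the plan says.** **The rule specific to non-responders.** Protocol 4.1 says that if hematologic response is still absent when it is reassessed after the three added cycles, "the patient will be removed from treatment and followed for survival". The Protocol Summary and SAP 1.1 repeat this.

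**The general rule for stopping without PD.**
- Protocol 4.1, a little further on: "If patients are removed from treatment for unacceptable toxicity or reasons other than PD, they will continue in PFS follow-up until documented disease progression", or until subsequent antineoplastic therapy.
- Protocol 4.3: "Patients who stop treatment for any reason other than disease progression will continue in PFS follow-up", with visits every 6 weeks.
- Protocol 7.5.12.1 asks for the M-protein, immunofixation and free light chain tests every 6 weeks in a patient who is off treatment and has not progressed.
- Protocol 7.5.17: "Patients who do not develop PD will continue to have PFS follow-up visits".
- Schedule of Events footnote e runs PFS follow-up from End of Treatment (EOT) to PD or new therapy. Footnote f says of the survival contacts: "Conducted every 12 weeks (± 1 week) after PD or the initiation of subsequent antineoplastic therapy".

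The Protocol Summary also conflicts with itself, because it separately requires hematologic assessments every 6 weeks after EOT until PD or new therapy.

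**The analysis rules.** In SAP 5.8.1 a living patient with no PD and no new therapy is censored at the last response assessment, and a patient who starts new therapy is censored at the last assessment before it. Death without PD or new therapy is an event for PFS but is censored for time to progression. No rule covers patients whose assessments stop by design.

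**The concern.** A patient with stable disease and no response after Cycle 6 leaves treatment for a reason other than PD. Section 15.8 defines PD by rises in M-protein or free light chain, so lack of response is not PD. Two rules therefore apply to the same patient, and they differ on whether progression is looked for afterwards.

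This is more than a clerical matter. The survival sentence is the one written specifically for non-responders, so a site could reasonably let it override the general rule. Survival data may be collected by telephone or mail, without any disease assessment. Progression would then go unobserved in one outcome-defined group while it was still being assessed in responders. Time to progression and PFS are named secondary endpoints. With at most 50 patients at about 10 centers, different readings at different sites could matter. Missed PD would also slow the count towards the 75%-with-PD trigger for the study report, although the 12-month alternative limits any delay.

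**Working it through.** **1. Is there a stated figure to reproduce?** None for PFS or time to progression. The only design probabilities concern organ response: at least 2 of 8 at 35% gives 0.831 (stated 83%), and at least 2 of 14 at 20% gives 0.802 (stated 80%). Both reproduce, and neither bears on this point.

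**2. When would assessment end?** Cycle 6 ends on day 6 × 28 = 168, or 168/30.44 = 5.5 months. The last Cycle 6 dose is on day 5 × 28 + 15 = 155. Footnote d places EOT at least 30 days after the last dose unless new therapy starts first, so at about day 185, or 6.1 months.

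**3. Size, under assumptions.** The documents give no progression or death rates by response. Assumed inputs:
- non-responders are 30%, 50% or 70% of patients;
- latent median time to PD is 18 months in responders and 18, 12 or 6 months in non-responders;
- latent median time to death is twice the PD median in each group, independent of PD;
- no one starts new therapy;
- the data cut falls 12 to 36 months after entry (24 months of enrolment plus 12).

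Kaplan-Meier estimates at 12 months, from 400,000 simulated patients under the SAP censoring rules. The survival wording is applied from day 168:

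| Non-responders | Their PD median (months) | TTP, full follow-up | TTP, survival wording | PFS, full follow-up | PFS, survival wording |
|---|---|---|---|---|---|
| 30% | 18 | 0.629 | 0.629 | 0.500 | 0.492 |
| 50% | 18 | 0.629 | 0.629 | 0.499 | 0.485 |
| 70% | 18 | 0.631 | 0.630 | 0.501 | 0.475 |
| 30% | 12 | 0.593 | 0.612 | 0.456 | 0.468 |
| 50% | 12 | 0.568 | 0.599 | 0.427 | 0.444 |
| 70% | 12 | 0.541 | 0.585 | 0.398 | 0.416 |
| 30% | 6 | 0.531 | 0.569 | 0.387 | 0.414 |
| 50% | 6 | 0.460 | 0.526 | 0.312 | 0.356 |
| 70% | 6 | 0.383 | 0.481 | 0.237 | 0.295 |

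(TTP = proportion without progression, deaths censored.)

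**4. Hand check of the row with 50% and 6 months.** With the death hazard half the PD hazard, the PFS hazard is 1.5 times the PD hazard in each group.
- Full PFS at 12 months: 0.5 × 2^(−1.5×12/6) + 0.5 × 2^(−1.5×12/18) = 0.0625 + 0.25 = 0.3125.
- PD is two thirds of the hazard in both groups, so full TTP = 0.3125^(2/3) = 0.461.
- At 5.52 months, PFS = 0.5 × 2^(−1.38) + 0.5 × 2^(−0.46) = 0.556, so TTP = 0.556^(2/3) = 0.676.
- Under the survival wording only responders then remain at risk of an observed PD: 0.676 × 2^(−(12−5.52)/18) = 0.676 × 0.779 = 0.527, against 0.526 simulated.

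**5. Effect of the EOT assessment.** Repeating the check with the cut at 6.08 months, PFS is 0.526, TTP is 0.526^(2/3) = 0.652, and 0.652 × 2^(−5.92/18) = 0.519. The excess falls from about 6.6 to 5.8 points.

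**6. Reading.** When non-responders progress faster, TTP is too high by 1.9 points (0.612 − 0.593) to 9.8 points (0.481 − 0.383), and PFS by 1.2 points (0.468 − 0.456) to 5.8 points (0.295 − 0.237). With equal hazards TTP is unbiased and PFS falls by about 1 to 3 points, because non-responders who die stay in as events while those who survive are censored at Cycle 6.

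**The case against.** The strongest reply is that the operative text already settles the matter. The survival sentence appears in design overviews, whereas the schedule, 7.5.12.1 and 7.5.17 are what sites work from, and all of them keep a patient without PD in PFS follow-up. Under footnote f such a patient has no survival-only track to enter. The protocol also labels its whole follow-up period as progression-free and overall survival, so the phrase can be read loosely. This stands to the extent that many sites would probably do the PFS visits. It does not remove the conflict: footnote e speaks of OS follow-up for patients who stop because of PD, the schedule has a separate survival row, and the sentence aimed at non-responders mentions no PFS visits.

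A reader might infer that non-responders are followed for survival only. The documents never say only. A reader might also infer that PFS and time to progression are in fact biased in the drug's favour. That needs two further conditions: sites act on the survival wording, and non-responders progress faster. The Protocol background says that hematologic response predicts survival, which makes the second plausible, but no rate is given. Nor are the endpoints affected alike, since deaths without new therapy remain PFS events.

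The effect is also small beside sampling error. At a 12-month estimate of 0.46, the approximate 95% half-width is 1.96 × √(0.46 × 0.54/50) = 0.14 with 50 patients and 0.19 with 26. That lowers the urgency, but the sampling error will be reported and a gap in ascertainment may not be.

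**Conclusion.** The contradiction is real and should be resolved. It lies within Protocol 4.1 and between the three survival sentences and the follow-up rules in 4.3, 7.5.12.1, 7.5.17 and footnotes e and f.

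The bias is conditional. If the survival wording is applied and non-responders progress faster, time to progression is informatively censored from about 5.5 to 6 months and PFS is partly affected. The sizes, about 2 to 10 points and 1 to 6 points at 12 months, are illustrations that rest wholly on the assumed shares and hazards. The direction for PFS can reverse when hazards are equal.

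The practical exposure is mainly the hematologic endpoints, because SAP 5.8.2 names only those and overall survival for Kaplan-Meier analysis and puts the organ time-to-event endpoints in listings. All are secondary and descriptive, with no formal tests. The MTD and RP2D do not depend on them.

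**What to change.** Reconcile the sentence in the Protocol Summary, Protocol 4.1 and SAP 1.1 with the follow-up rule in the rest of 4.1, 4.3 and 7.5.17: a patient removed for lack of hematologic response without PD remains in PFS follow-up until PD or subsequent antineoplastic therapy, and then enters OS follow-up. This concerns data collection only and leaves the treatment-removal rule as it is.

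The cost is one sentence in three places. The 6-weekly hematologic and 6-monthly organ assessments are already scheduled for other patients who stop without PD. If some non-responders have already been followed for survival alone, the study report should give their number and last assessment dates.

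The change does not remove all informative censoring. Non-responders who start new therapy are still censored at the last assessment before it under SAP 5.8.1, and 7.5.17 ends organ assessments at hematologic progression. Reporting the number censored for new therapy, by response status, would let readers judge what remains.

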4.2 Number of Patients

As many as 50 patients will be enrolled in this study. As many as 30 patients will be enrolled in the dose-escalation portion of the study. Because approximately 6 patients in the dose-escalation part of the study will be included in the expansion cohort, approximately 20 patients will be enrolled in the expansion part of this study after taking the dropout rate into consideration. Patients will be enrolled from approximately 10 centers in North America and Europe. Enrollment is defined as the time the patient receives the first dose of any study drug.

4.3 Duration of Study

The duration of enrollment will be approximately 24 months.

Patients who have a response to treatment may remain on treatment for a maximum of 12 cycles or until the occurrence of PD or unacceptable toxicity, whichever occurs first. Patients who stop treatment for any reason other than disease progression will continue in PFS follow-up and be seen every 6 weeks until documented disease progression. After disease progression, all patients will continue to the OS follow-up part of the study and will be contacted every 12 weeks.

Delayed treatment-related AEs will be followed for 30 days after last dose of study drug or until initiation of subsequent antineoplastic therapy. The analyses for the clinical study report will be conducted after 75% of patients have PD or 12 months after last patient is enrolled, whichever occurs first in the study.

It is anticipated that this study will last for approximately 84 months. The duration of follow-up for overall survival will be 60 months after the last patient enters the study. Treatment may be continued in this study or in a MLN9708 rollover study, if and when such a study is made available, upon request by the investigator and agreement by the project clinician.

5. STUDY POPULATION

Adult patients with biopsy-proven systemic AL amyloidosis with relapsed or progressive disease despite prior therapy will be enrolled.

5.1 Inclusion Criteria

1. Male or female patients 18 years or older.
2. Histologic diagnosis of AL amyloidosis, confirmed by pathology-positive Congo red stain with green birefringence on polarized light microscopy, with evidence of measurable clonal disease according to standardized criteria^(54, 55, 56) that requires active treatment (see Section 15.2 for amyloid typing).
3. Patients will have a measurable disease as defined by serum differential free light chain concentration (dFLC, difference between amyloid forming and nonamyloid forming free light chain [FLC]) ≥ 40 mg/L.
4. Percentage of plasma cells $< 30\%$ in the bone marrow aspirate and biopsy.
5. Patients must have objective, measurable major organ (heart or kidney) involvement.
 - a. renal: albuminuria higher than 0.5 g/day in 24-hour urine analysis.
 - b. cardiac: involvement is defined as the presence of a mean left ventricular wall thickness on echocardiogram more than 12 mm in the absence of a history of hypertension or valvular heart disease, or unexplained low voltage (< 0.5 mV) on electrocardiogram; or NT-proBNP > 332 ng/L in the absence of renal failure (estimated glomerular filtration rate [eGFR] < 45 mL/min/1.73 m²).

In addition, patients can also have amyloidosis organ involvement in such organ systems as liver/GI tract, peripheral nerves, or soft tissue. Skin purpura, carpal tunnel syndrome, or the presence of vascular amyloid on a bone marrow biopsy alone are not sufficient to meet criteria for “symptomatic organ involvement”. Patient may present with **any** of the following amyloid-related organ involvement as defined below:

- a. hepatic: hepatomegaly on physical examination with alkaline phosphatase $> 1.5 \times$ the upper limit of normal (ULN).
- b. gastrointestinal: direct biopsy verification of amyloid involvement with symptoms such as gastrointestinal bleeding (confirmed by tissue biopsy) or diarrhea (at least 4 stools per day). A positive GI biopsy change is not sufficient.
- c. autonomic or peripheral neuropathy: based on clinical history, autonomic dysfunction with orthostasis, symptoms of nausea or dysgeusia, gastric atony by gastric emptying scan, diarrhea or constipation, or abnormal sensory and/or motor findings on neurologic examination.
- d. soft tissue and lymphatic: based on physical examination findings (macroglossia, shoulder pad sign, raccoon eyes, carpal tunnel syndrome, synovial enlargement, or firm enlarged lymph nodes) or biopsy.

6. AL Amyloidosis Risk stage I or II disease.

Staging system defined by: NT-proBNP cut off of < 332 pg/mL and troponin T cut-off of 0.035 ng/mL as thresholds. Stage I, both under threshold; Stage II, either troponin or NT-proBNP [but not both] over threshold; if troponin T not available at local institution, troponin I may be used, but threshold is < 0.1 ng/mL. ⁽⁵⁷⁾

7. Must be relapsed or refractory after at least 1 prior therapy for AL amyloidosis and, in the investigator's opinion, requires further treatment.

NOTE: If a patient has received a transplant as his/her first therapy, he/she must be at least 3 months posttransplantation and recovered from the side effects of the stem cell transplant.

Any patient who was not a candidate for high-dose therapy and was unable to tolerate an alkylating agent plus a corticosteroid (eg, melphalan plus prednisone) or patients who are intolerant to an alternative prior therapy after receiving at least 1 cycle of such therapy because of severe adverse events

(eg, hypersensitivity reaction) also can be considered for enrollment after discussion with the Millennium clinician.

8. Patients must have an Eastern Cooperative Oncology Group (ECOG) status of 0 to 2 (see Section 15.3)
9. Clinical laboratory values as specified below within 3 days before the first dose of study drug (unless otherwise noted):
 - a. echocardiographic ejection fraction $\geq 40\%$ within 28 days before the first dose of study drug.
 - b. platelet count $\geq 75 \times 10^9/\text{L}$.
 - c. neutrophil count $\geq 1.0 \times 10^9/\text{L}$.
 - d. total bilirubin $\leq 1.5 \times \text{ULN}$.
 - e. alkaline phosphatase $\leq 5 \times \text{ULN}$.
 - f. alanine aminotransferase (ALT) and aspartate aminotransferase (AST) $\leq 3 \times \text{ULN}$.
 - g. eGFR $\geq 45 \text{ mL/min}/1.73 \text{ m}^2$ (see Section 15.1 for the Equation to Estimate Glomerular Filtration Rates).
10. Female patients who:
 - Are postmenopausal for at least 1 year before the screening visit, OR
 - Are surgically sterile, OR
 - If they are of childbearing potential, agree to practice 2 effective methods of contraception, at the same time, from the time of signing the informed consent through 30 days after the last dose of study drug, or agree to completely abstain from heterosexual intercourse.
11. Male patients, even if surgically sterilized (ie, status postvasectomy), who:
 - Agree to practice effective barrier contraception during the entire study treatment period and through 4 months after the last dose of study drug, OR
 - Agree to completely abstain from heterosexual intercourse.
12. Voluntary written consent must be given before performance of any study-related procedure not part of standard medical care with the understanding that consent may be withdrawn by the patient at any time without prejudice to future medical care.

